k Blood Specimens for the determination of the FAST PV and mGFR will be taken pre-dose and at 15 ( $\pm 5$ ), 30 ( $\pm 5$ ), 60 (+ 30) and 180 (+ 120) minutes post dose on Day 1 and Day 3. Note that the 30 minute blood draw must be at least 10 minutes after the 15 minute blood draw, and the 180 minute blood draw must be at least 100 minutes after the 60 minute blood draw.

l See Table 10 for the Adjudication Committee Evaluation Questions; Adjudication Committee meets after all collected data available.

m See Table 11 for Details of Pregnancy test

\*will be collected retrospectively after study inclusion

Table 2: Structural heart disease Criteria
Last documented left ventricular ejection fraction (%)
Evidence of left ventricular hypertrophy
Evidence of left atrial enlargement
Evidence of diastolic dysfunction
Other cause of heart failure

Table 3: Demographics
ID
Date of admission
Date of inclusion (Day 1)
Date of birth
Age at inclusion (years)
Gender
Ethnicity

Table 4: Comorbidities
Free text documentation of all comorbidities
In addition, the following comorbidities are recorded systematically (by "yes" or "no" answers):
CKD stage
previous myocardial infarction
Hypertension
Preexisting coronary heart disease
Preexisting congestive heart failure
Previous hospitalization for acute decompensated heart failure?

Diabetes mellitus Cerebral vascular disease Peripheral arterial occlusive disease Other comorbidities
--

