**Table 10: Adjudication Committee Evaluation**

Would FAST GFR and PV measurements have changed clinical management overall?

Would the FAST GFR and PV measurement on day 1 have led to applying a different diuretics dosage between day 1-3?

Would the FAST GFR and PV measurement on day 3 have led to applying a different dosage between day 3-5?

Would the FAST GFR and PV measurement on day 1 have led to choosing dialysis/ultrafiltration instead of diuretics escalation between day 1-3?

Would the FAST GFR and PV measurement on day 1 have led to choosing diuretics escalation instead of dialysis/ultrafiltration between day 1-3?

Would the FAST GFR and PV measurement on day 3 have led to choosing dialysis/ultrafiltration instead of diuretics escalation between day 3-5?

Would the FAST GFR and PV measurement on day 3 have led to choosing diuretics escalation instead of dialysis/ultrafiltration between day 3-5?

\*Responses will be collected as a Yes/No, with an additional free text section available to record details to substantiate the response

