- To evaluate (by an adjudication committee) whether clinical decision making would have been affected by adding FAST GFR and PV measurements to clinical routine including the following questions:
  - Would FAST GFR and PV measurements have changed clinical management overall?
  - Would the FAST GFR and PV measurement on day 1 have led to applying a different diuretics dosage between day 1-3?
  - Would the FAST GFR and PV measurement on day 3 have led to applying a different diuretics dosage between day 3-5?
  - Would the FAST GFR and PV measurement on day 1 have led to choosing dialysis/ultrafiltration instead of diuretics escalation between day 1-3?
  - Would the FAST GFR and PV measurement on day 1 have led to choosing diuretics escalation instead of dialysis/ultrafiltration between day 1-3?
  - Would the FAST GFR and PV measurement on day 3 have led to choosing dialysis/ultrafiltration instead of diuretics escalation between day 3-5?
  - Would the FAST GFR and PV measurement on day 3 have led to choosing diuretics escalation instead of dialysis/ultrafiltration between day 3-5?

To evaluate this endpoint an adjudication committee will be convened to analyse the outputs of the study after its completion. The goal of the adjudication committee is to the best of their ability describe any changes in treatment they would have made to each patient based had the mPV and mGFR metrics been available during the episode of care. No clinical decisions will be made based on the results generated by the FAST PV and mGFR Technology as results will not be made available to the treating physicians and will only be released to the adjudication committee after the last patient has been discharged. We will calculate absolute and relative frequencies of the “yes”-answers to the questions specified above together with 95% confidence intervals.

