- To evaluate whether ranges of mPV (low mPV, normal mPV, high mPV) and/or mTBV (low mTBV, normal mTBV, high mTBV) on days 1 and 3 are associated with subjectively reported symptoms (PGA, dyspnea, dizziness, nausea) determined using patient symptom assessment sheets within the following 24-48 hours.

- 
- To evaluate whether patients with low mPV or low mTBV on day 1 or on day 3 are at risk of developing low-output complications within the next 24-48 hours (subjectively reported dizziness/nausea, PGA, hypotension, need for iv-fluid therapy).
  - To evaluate whether patients with a high mPV or a high mTBV on day 1 and/or day 3 are at risk of being refractory to diuretic therapy (e. g. require dosage increases of furosemide/torsemide, require ultrafiltration/RRT within the next 24-48 hours, fail to improve subjectively in PGA and dyspnea scales).
  - To evaluate whether the time course of ePV and eTBV from day 1 to day 3 adequately reflect the time course of mPV and mTBV at these time points.
  - To evaluate whether the change of mPV and mTBV from day 1 to day 3 is predictive of length of stay, dialysis/ultrafiltration requirement, or rehospitalization within 30 days, or mortality.
  - To evaluate whether the time course of mGFR from day 1 to day 3 correlates temporally with or predicts the time course of eGFR within the next 24-48 hours.
  - To evaluate (by an adjudication committee) whether clinical decision making would have been affected by adding FAST GFR and PV measurements to clinical routine including the following questions:
    - Would FAST GFR and PV measurements have changed clinical management overall?
    - Would the FAST GFR and PV measurement on day 1 have led to applying a different diuretics dosage between day 1-3?
    - Would the FAST GFR and PV measurement on day 3 have led to applying a different diuretics dosage between day 3-5?
    - Would the FAST GFR and PV measurement on day 1 have led to choosing dialysis/ultrafiltration instead of diuretics escalation between day 1-3?
    - Would the FAST GFR and PV measurement on day 1 have led to choosing diuretics escalation instead of dialysis/ultrafiltration between day 1-3?
    - Would the FAST GFR and PV measurement on day 3 have led to choosing dialysis/ultrafiltration instead of diuretics escalation between day 3-5?
    - Would the FAST GFR and PV measurement on day 3 have led to choosing diuretics escalation instead of dialysis/ultrafiltration between day 3-5?

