or TBVS between Day 1 and 3 had significantly different percentage change of mGFR between Day 1 and Day 3 compared to patients with a high PVS or TBVS and an increasing PVS between Day 1 and 3, t-Tests or Mann-Whitney-U-tests will be used depending on the distribution of the values.

To evaluate whether Patients with a low PVS or TBVS on Day 1 (<-10%) and an increasing PVS or TBVS between Day 1 and 3 had significantly different percentage change of mGFR between Day 1 and Day 3 compared to patients with a low PVS or BCS and a decreasing PVS between Day 1 and 3, t-Tests or Mann-Whitney-U-tests will be used depending on the distribution of the values.

To evaluate whether patients with an improving (i.e. increasing) mGFR from day 1 to day 3 differ significantly from patients with a worsening (i.e. decreasing) mGFR regarding baseline characteristics (see chapter 4.1), mPVS, mTBVS, ePVS, eTBVS, and remaining length of stay appropriate tests depending on the distribution will be used (t-Test or Mann-Whitney-U-test for continuous variables and chi-square tests or Fisher-Boschloo-tests for categorical variables).

To evaluate whether disagreement between the physicians response to the question what they thought the intravascular volume of the patient was doing (increasing, decreasing, no change, treating physicians assessment Day 3) and the direction of measured change in TBVS is associated with a longer remaining length of stay, a t-test or Mann-Whitney-U-test depending on the distribution will be used. A measured change in TBVS of more than 5% between Day 1 and 3 was determined as a significant change.

To evaluate (by an adjudication committee) whether clinical decision making would have been affected by adding FAST GFR and PV measurements to clinical routine, the following questions were to be answered:

- How would you alter the intensity of Diuretic Therapy given on Day 1 and Day 3?
- How would you alter the intensity of RAASI Therapy given Day 1 and Day 3?  
How would you alter the intensity of Beta Blocker Therapy given Day 1 and Day 3?
- How would you alter the intensity of other GDMT given Day 1 and Day 3?

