To evaluate this endpoint an adjudication committee will be convened to analyse the outputs of the study after its completion. The goal of the adjudication committee is to the best of their ability describe any changes in treatment they would have made to each patient had the mPV and mGFR metrics been available during the episode of care. No clinical decisions will be made based on the results generated by the FAST PV and mGFR Technology as results will not be made available to the treating physicians and will only be released to the adjudication committee after the last patient has been discharged.

The scale to define the intensity of changes reaches from 1 to 5 meaning from much less intense to much more intense (3 is no change).

Absolute and relative frequencies of the changes to the questions specified above will be calculated for the whole assessment and separately for Day 1 and Day 3.

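### SAP 7.7.1 replaces the seven Yes/No adjudication questions of SAP 1.1 with four intensity ratings, drops the protocol's 95% confidence intervals, and section 8 does not declare the change

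*SAP*

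**What the plan says.** **Protocol.** The synopsis, section 4.2, Table 10 and section 14 all carry the same seven questions. The schedule gives them to the committee: "See Table 10 for the Adjudication Committee Evaluation Questions; Adjudication Committee meets after all collected data available". Table 10 fixes the answer format: "Responses will be collected as a Yes/No, with an additional free text section available to record details to substantiate the response". Section 14 then plans counts and percentages of the yes-answers "to the questions specified above together with 95% confidence intervals".

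**SAP 1.1.** The objective keeps all seven, from "Would FAST GFR and PV measurements have changed clinical management overall" to items such as "Would the FAST GFR and PV measurement on day 1 have led to choosing dialysis/ultrafiltration instead of diuretics escalation between day 1-3".

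**SAP 7.7.1.** For the same objective the analysis section lists four different items. The first is "How would you alter the intensity of Diuretic Therapy given on Day 1 and Day 3"; the others ask the same of RAASI, beta blocker and other GDMT therapy. Each is scored from 1 to 5, with 3 meaning no change. Counts and percentages are planned for each day and for the two days combined. No confidence interval is mentioned.

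**SAP 4.3, section 8 and version history.** The lists of secondary variables contain no adjudication variable. Section 8 declares four changes from the protocol: no variable selection, volume status classified by mPVS and mTBVS, Bland-Altman analysis in place of t-tests and curve characteristics, and the use of haemoglobin and cystatin C. None concerns adjudication, and the version history does not mention it either.

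**The concern.** An SAP should analyse the questions that its own objective asks. Here the objective and the analysis section name different questions, in a different response format and with a different statement of precision. A statistician who follows 7.7.1 exactly would produce no proportion for most of the questions in 1.1. A reader of the report would find a listed objective without its result and no explanation in the section meant for departures from the protocol.

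The endpoint matters to the trial's argument. The protocol's hypotheses include that clinical decisions would have been improved in some patients had the measurements been available, and the adjudication bears on that most directly.

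**Working it through.** There is no planned figure to reproduce: the protocol gives no formal sample size calculation, and this point rests on none. The check is a side-by-side count, followed by an illustration of what the dropped intervals would show.

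**Step 1. Count the items.** SAP 1.1: 1 overall + 2 diuretic dosage + 4 dialysis or ultrafiltration = 7 questions. SAP 7.7.1: 4 ratings, each for Day 1 and Day 3, so 4 × 2 = 8 ratings per patient.

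**Step 2. Match them, counting only statistical analyses planned in the SAP.**

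| Question in SAP 1.1 | Number | Counterpart in SAP 7.7.1 |
|---|---|---|
| Management changed overall | 1 | None: no item asks it, and no rule derives it from the ratings |
| Different diuretic dosage (days 1-3, days 3-5) | 2 | Partial: a diuretic rating other than 3 could stand for it, but the SAP gives no such rule |
| Dialysis or ultrafiltration against diuretic escalation (both directions, both periods) | 4 | None |

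No counterpart: 1 + 4 = 5 of 7. Partial proxy: 2 of 7. Same wording: 0 of 7.

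**Step 3. Look for the missing analyses elsewhere.** SAP 4.3.1 and 4.3.2 contain no adjudication variable, so no other section fills the gap.

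**Step 4. Compare the precision statements.** Protocol section 14 attaches 95% intervals to the yes-proportions. SAP 7.7.1 attaches none to the ratings, although it keeps a 95% interval for the Obuchowski accuracy measure in the same section.

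**Step 5. What the intervals would convey.** The exact (Clopper-Pearson) limits for x yes-answers among n patients are the 0.025 quantile of Beta(x, n − x + 1) and the 0.975 quantile of Beta(x + 1, n − x). For x = 0 the lower limit is 0 and the upper limit reduces to 1 − 0.025^(1/n). With the planned n = 50 and one committee answer per patient:

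- 0/50: upper limit 1 − 0.025^(1/50) = 7.1%, so 0 to 7.1%
- 5/50 (10%): 3.3% to 21.8%
- 10/50 (20%): 10.0% to 33.7%
- 25/50 (50%): 35.5% to 64.5%

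These counts are illustrative and predict nothing.

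**The case against.** **The analyses are descriptive.** True, but the protocol is equally descriptive and still plans intervals for this endpoint. Descriptive status does not explain their absence.

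**The broad objective is still addressed.** This stands. SAP 7.7.1 introduces the ratings under the same objective and asks the committee to "describe any changes in treatment they would have made to each patient had the mPV and mGFR metrics been available". The list of seven is also introduced as included questions, not as a closed set. The added RAASI, beta blocker and GDMT ratings are therefore no fault. The fault is that listed questions were left out and the change was not declared.

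**The committee's report covers the rest.** The protocol synopsis has the committee write a summary report on the secondary endpoints, which would take in all seven questions. A narrative does not replace the proportions with intervals of protocol section 14.

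**Intervals can be worked out from published counts.** For the ratings this is right, and the loss there is small. It does not help with Yes/No answers that are not tabulated.

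**The instrument may have been revised.** SAP section 3 speaks of enrolment in the past tense, and 7.7.1 does the same of the four questions. The documents do not show that the Table 10 answers exist, so restoring them can only be conditional.

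A reader might also infer that a rating other than 3 merely records disagreement with the therapy given, and so says nothing about the FAST measurements. The framing in 7.7.1 runs against that. A reader might equally infer that combining Day 1 and Day 3 gives an interval that is too narrow. No interval is planned for the combined figure, and the direction of any error would depend on how a patient's two ratings are correlated.

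**Conclusion.** The point holds as a mismatch within the SAP and an undeclared departure from the protocol. Followed as written, SAP 7.7.1 gives no statistical result for five of the seven questions in SAP 1.1, only an unmapped proxy for the other two, and none of the confidence intervals planned for this endpoint.

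The count of five rests on one rule: only statistical analyses in the SAP are counted, not the committee's narrative report. The intervals shown assume 50 adjudicated patients and one answer per patient.

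The SAP should be corrected, but the trial's main result is not at risk: the endpoint is secondary and descriptive, and the primary conclusion on safety and marker stability does not depend on it. The documents do not show why the questions were changed, and nothing in them supports reading the change as driven by results.

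**What to change.** 1. In SAP section 8, declare and justify the change of questions, response format and interval plan, and reconcile section 1.1 with 7.7.1.
2. If the Table 10 answers were collected, tabulate for each question the yes-proportion per patient, with its denominator and an exact 95% confidence interval. The denominator matters on Day 3, since SAP 7.5 foresees missed second doses. If the answers were not collected, say so in section 8, amend the objective in 1.1, and label any answers obtained later as retrospective.
3. Keep the four ratings as supplementary results. Give the proportion with a score other than 3, with a 95% interval, for Day 1 and Day 3 separately. For the combined assessment give counts only.
4. Add the adjudication variables to SAP 4.3.1.

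The cost is SAP wording and a few tables. If answers have to be obtained now, some committee time is added; it cannot be sized because the committee's size is not stated. No patient procedure is involved.

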### 7.7.2 Safety/Tolerability

#### **Adverse events**

AEs and SAEs will be regarded for safety analysis if they are treatment emergent, i.e. if they were not present prior to the first application of VFI or in case they were present and are worsening after the first application of VFI.

All AEs, whether or not they are considered to be related to treatment are reported.

They are listed by subject providing the following information:

- Age, sex, weight, BMI
- The adverse event (reported term by investigator, MedDRA preferred term, System Organ Class)
- Date of onset
- Duration of the adverse event
- Severity
- Seriousness (serious/non-serious)
- Action taken
- Outcome
- Causality assessment

The adverse events are displayed in summary tables as follows:

- A table of the preferred terms of all AEs will be presented including the number and percentage of subjects in whom at least one event with the respective preferred term (PT) occurred. The PTs will be grouped by MedDRA System Organ Class (SOC) and sorted by frequency.
- Additionally, the number and percentage of subjects in whom at least one event in the respective SOC occurred will be given.
- The tables above will be additionally divided into the defined severity categories grouped by relatedness of the event to VFI.

Every table will be produced for the following AE sets:

- All AEs
- AEs for which a relationship to formula intake was considered to be related by the investigator

Such AEs which were documented as SAEs will be reported in the same way as the AEs.

Every table will be produced for the following SAE sets:

- All SAEs
- SAEs for which a relationship to VFI cannot be ruled out
- All SAEs with outcome death

Additionally, all deaths during the study and deaths that resulted from a process that began during the study are listed by subject.

### Laboratory parameters

Laboratory measurements that were study related will be analysed descriptively at each visit.

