#### **3.1.3.4 Phase 2b Study at University of Alabama at Birmingham and ICON**

The Phase 2b study was a prospective, open-label study designed to evaluate the safety, tolerability, PK, and pharmacodynamics (PD) of FAST PV and mGFR Technology in healthy patients and patients with varying degrees of renal impairment. A total of 32 patients were planned to be enrolled in 4 cohorts of up to 8 patients/patients each. Healthy patients in Cohorts 1 and 2 had an  $eGFR \geq 60$  mL/min/1.73 m^2; patients with impaired renal function in Cohort 3 had an  $eGFR \geq 30$  and  $< 60$  mL/min/1.73 m^2; and patients with impaired renal function in Cohort 4 had an  $eGFR \geq 15$  and  $< 30$  mL/min/1.73 m^2. Patients in Cohort 1 received a single dose of VFI followed 130 minutes later by a 350 mL infusion of 5% albumin in normal saline over 30 minutes on day 1. Patients in Cohort 2 received a dose of VFI followed 160 minutes later by a single dose of iohexol on day 1 and a second dose of VFI 24 hours following the initial dose of VFI. Patients in Cohorts 3 and 4 received a single dose of VFI followed 160 minutes later by a single dose of iohexol on day 1.

The pharmacokinetics of FD001 and FD003 showed that the clearance of FD001 was proportional to kidney function with urine clearances of 59.955 mL/min, 25.919 mL/min and 12.635 mL/min for cohorts 2, 3, and 4 respectively, when using 0 to 2 hour data. Following the end of the bolus injection, the plasma concentration of the FD001 decreased following a multi-exponent and first order elimination curve. Average measured GFR for cohorts 2, 3 and 4 were 87 mL/min, 48 mL/min, and 27 mL/min respectively.

The FD003 volume estimates indicated that FD003 appeared to occupy a volume of space equal to the plasma volume (Figure 4). FD003 had determined elimination half-lives of 95.3, 99.1, and 106 hours for Cohorts 2, 3, and 4, respectively. These rates were similar across the renal functions studied which indicates the marker's non-renal clearance is preserved in kidney failure patients.

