Cohort 1 used FD003 to monitor a change in volume induced by the infusion of 350 ml of 5% albumin solution given over 30 minutes. At 5 minutes post completion of the infusion, the average plasma volume increase was 324 ml with an SD of 49mL, showing excellent accuracy for following a change in plasma volume. By 30 minutes post infusion, the average volume increase from baseline was reduced to 224ml showing that FD003 was being retained within the vasculature even though the 5% Albumin solution was slowly distributing into the interstitial space. This cohort was not used for PK due to the complication of accounting for the additional volume infused.

The FAST VFI was generally safe and well tolerated in healthy patients in Cohorts 1 and 2 and in patients with impaired renal function in Cohorts 3 and 4. No severe or serious TEAEs, TEAEs leading to study drug discontinuation, or deaths were reported during the study. Overall, the majority of TEAEs reported were mild in severity. Three patients in Cohort 4 had a TEAE of blood creatine phosphokinase increased related to clinically significant abnormal creatine kinase levels. All 3 TEAEs of blood creatine phosphokinase increased were mild in severity and considered by the investigator to be possibly related to study drug. There were no other clinically significant abnormal clinical laboratory values. There were no clinically significant abnormal ECG or vital signs measurements, nor were there clinically meaningful trends identified in observed values or changes from baseline. There were no clinically significant abnormal physical examination findings.

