## **7.1 Recruitment procedures and informed consent process**

The Principal Investigator, his or her proxy / designee and the member of the trial team will have the full responsibility to screen for suitable patients.

The study group consists of nephrologists ([name]) and cardiologists ([name]). In our hospital (Charité - Universitätsmedizin) patients with acute decompensated heart failure (HF) are usually admitted to the cardiology departments or to the nephrology departments (if renal dysfunction is the leading cause for HF decompensation). Admission to the hospital may occur by direct referral from an outpatient physician or after initial evaluation and treatment at the emergency room. Since we plan to enroll patients with acute decompensated heart failure across a wide spectrum of renal function, we will enroll patients from both the cardiology and nephrology departments.

To facilitate effective screening, a designated study physician will work with treating physicians at the nephrology and the cardiology departments on a daily basis to identify patients with acute decompensated heart failure. All patients with a diagnosis of acute decompensated heart failure or "hydropic decompensation" (a frequently used clinical designation for acute decompensated heart failure in Germany) will be identified by the study physician and an initial discussion regarding study participation will take place between the study physician and the treating physicians at the departments of cardiology or nephrology. The study physician will then approach these patients and inform them about the study, ask for their participation and provide them with patient information material regarding the study. On the next morning, having allowed the patient a sufficient time period to reflect on study

participation, written informed consent will be obtained. This day will be designated "Day 1" of the study and patients will be evaluated and treated according to study protocol.

A screening log for documentation of these patients will be used. All pre-screened patients will be documented in the screening log and assigned a screening number.

Patients who do not refuse the trial will be asked to participate and the written informed consent could be given by the patient.

During the initial consultation, the following will be performed:

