### **Size Estimation**

We plan to enrol 50 eligible patients. Due to the explorative nature of this phase II study a formal sample size calculation is not possible. However, the sample size of 50 patients is sufficient to guarantee reasonable accuracy with respect to the main objectives of the trial as specified below.

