### Sample size

The primary objective is to assess the safety and function of the FAST PV and mGFR Technology in hospitalized patients with heart failure. This is a phase II trial. It is planned to enroll 50 eligible patients. No formal hypothesis test is performed to assess the primary objective. This is justified as follows:

1. Both function and safety cannot be uniquely assessed by one specific endpoint, but there exist several relevant endpoints and endpoint-related criteria which must be investigated in order to assess the global function and safety.
2. For reasons of feasibility, the studies sample size is limited to 50 patients which is an adequate number in the context of a phase II trial. However, this limited number does not allow to address a complex multiple testing problem with adequate power.

Therefore, all analyses are purely descriptive.

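### SAP 7.7.2 plans no within-patient CPK change, no threshold count and no display by renal function, so CPK rises not recorded as AEs may be diluted and a low-eGFR pattern would not be shown

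*SAP*

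**What the plan says.** **Earlier signal.** Protocol 3.1.3.4 (Phase 2b) reports: "Three patients in Cohort 4 had a TEAE of blood creatine phosphokinase increased related to clinically significant abnormal creatine kinase levels". All three events were mild and "considered by the investigator to be possibly related to study drug". The same section says that "patients with impaired renal function in Cohort 4 had an" eGFR of at least 15 and below 30. It reports no other clinically significant laboratory abnormality.

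**This trial.** Protocol 7.1 explains why both cardiology and nephrology departments recruit: "Since we plan to enroll patients with acute decompensated heart failure across a wide spectrum of renal function". Protocol 6.1.2 schedules a dose on Day 1 and again on Day 3. CPK is a study-specific test on Days 1, 3 and 5 (Protocol Table 7; SAP 4.3.2) and is not among the routine parameters in Protocol Table 8.

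**Analysis.** The laboratory paragraph of SAP 7.7.2 is one sentence: "Laboratory measurements that were study related will be analysed descriptively at each visit". SAP 7.1 sets the statistics for continuous variables: mean, SD, median, interquartile range and range. SAP 7.8 plans no subgroup analyses. CPK is not among the variables inspected for outliers in SAP 5.2.

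**AE route.** Protocol 10.1 and 10.9 have investigators review out-of-range values and record relevant ones as AEs. SAP 7.6 counts sure, probable and possible events as related. SAP 7.7.2 lists AEs by subject and tabulates them by preferred term, severity and relatedness.

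**The concern.** CPK is the one laboratory signal that the protocol reports from Phase 2b, and all its cases were at low eGFR. Cohort 4 received a single dose. The only Phase 2b cohort described as dosed twice (Cohort 2) had eGFR of 60 or above. The protocol therefore describes no repeat-dose CPK experience at low eGFR in that study, while this trial gives two doses to patients who may have low eGFR.

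With one arm, each patient's own Day 1 value is the natural internal comparator, and a per-visit summary discards it. Pooling all patients also mixes any low-eGFR patients with the rest. Missing secondary values are not replaced (SAP 5.1), so the Day 1, 3 and 5 summaries may describe different patients.

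At stake is a descriptive safety finding: whether CPK rises short of a recorded AE occur, and whether they cluster at low eGFR.

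**Working it through.** The plan has no figure to reproduce. N is 50 ("It is planned to enroll 50 eligible patients") and the protocol says that "a formal sample size calculation is not possible".

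**1. Earlier rate.** The numerator is 3. The actual size of Cohort 4 is not stated, only the plan: "A total of 32 patients were planned to be enrolled in 4 cohorts of up to 8 patients/patients each".
- If the cohort was full: 3/8 = 37.5%, exact (Clopper-Pearson) 95% CI 8.5% to 75.5%.
- If smaller: 3/7 = 42.9% or 3/6 = 50%.
- Over all 32 planned patients: 3/32 = 9.4% (2.0% to 25.0%).

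**2. Cases to expect here.** The number of patients with eGFR 15 to below 30 is not given, so take m = 5, 10 or 15 as a range. Expected cases are m × p, and P(at least one) = 1 − (1 − p)^m.

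| m | Expected at p = 0.375 | P(≥1) at p = 0.375 | P(≥1) at p = 0.085 |
|---|---|---|---|
| 5 | 1.9 | 0.905 | 0.36 |
| 10 | 3.8 | 0.991 | 0.59 |
| 15 | 5.6 | 0.999 | 0.74 |

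A repeat of the earlier rate would mean a handful of patients among 50.

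**3. What per-visit summaries would show.** The assumptions below are not from the documents: log-normal CPK, median 100 U/L, between-patient log-SD 0.6, per-measurement log-SD 0.18, 50 patients.
- *Fixed rise.* If 3 patients each rise by 300 U/L, the mean shift is 3 × 300 / 50 = 18 U/L. The assumed mean is 100 × exp((0.6² + 0.18²)/2) = 121.7 U/L, so the shift is 18/121.7 ≈ 15%. In simulation the median rises about 5% and the SD about 36%. The maximum rises by more than 30% in about 45% of runs.
- *Proportional rise.* With m = 5, 10 or 15 and 3/8 of them (2, 4 or 6 patients) rising 2- or 3-fold, 4,000 simulated trials per setting give a median rise of about 3% to 10% and a mean rise of about 4% to 24%. The maximum rises by more than 30% in 24% to 72% of runs.

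**4. What a paired ratio would show, same assumptions.** The log of the Day 3/Day 1 ratio has noise SD 0.18 × √2 = 0.255. For cut-off c and true fold-change f, P(flag) = 1 − Φ((ln c − ln f)/0.255).

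| Cut-off | Flagged by noise (f = 1) | f = 2 | f = 3 |
|---|---|---|---|
| 1.5 | 5.6%, or 2 to 3 of the 44 to 48 non-risers | 87% | over 99% |
| 2.0 | 0.3%, or about 0.2 of 50 | 50% | 94% |

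A doubling rule gives few false flags but misses half of true 2-fold rises. This is why the change and the ratio should be shown alongside the count.

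**The case against.** The strongest reply is that the AE route found the signal before and exists here. The Phase 2b cases were themselves reported as treatment-emergent AEs. Protocol 10.1 names significant changes from baseline or from the previous visit as one way to identify abnormal values, which is a within-patient review. A repeat of the Phase 2b events, judged possibly related, would enter the primary safety result under SAP 7.6. This stands. A reader might infer that a CPK effect would go unseen, and the documents do not support that.

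Three limits remain. The route depends on case-by-case judgement, and a rise attributed to the acute illness may not be recorded. The protocol's capture rules differ: the synopsis captures AEs related or possibly related to the injectate, while 10.9 requires all. The by-subject AE listing in SAP 7.7.2 carries age, sex, weight and BMI but no renal function.

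Other parts of the reply also stand:
- Per-visit statistics include SD and range, so dilution is partial. A claim that the pooled summaries will not move would be too strong.
- Primary safety is related AEs and SAEs. Laboratory values are secondary safety variables (SAP 4.3.2), so this is not a defect in the primary endpoint.
- Protocol 7.1 describes a wide spectrum of renal function and sets no target or stratum for eGFR 15 to below 30.
- Omitting subgroups is an explicit choice in a purely descriptive trial. A descriptive display by eGFR for one analyte does not conflict with that purpose.
- Early discharge could make the Day 5 sample differ, but the documents give no discharge figure to size this.

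**Conclusion.** The point holds as a reporting gap limited to CPK. SAP 7.7.2 specifies no paired change, no threshold count and no display by renal function for the one analyte with a reported Phase 2b laboratory signal. Two things are exposed: rises that investigators do not record as AEs, and any clustering at low eGFR.

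Under the assumptions above, a rise in 2 to 6 of 50 patients moves the pooled median by about 3% to 10%, while a paired ratio picks out most of the individual risers at a cut-off of 1.5. The low-eGFR count, the size of the rise and the CPK distribution are all assumed, and the denominator of 8 is a planned maximum. The figures illustrate the mechanism and do not predict a rate.

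A reader might also infer an established drug effect. The documents support only three mild events judged possibly related. The sample size is not affected.

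**What to change.** Add to SAP 7.7.2 one descriptive CPK table, using for each comparison only patients with both values:
- within-patient change and ratio from Day 1 to Day 3 and from Day 1 to Day 5;
- number and percentage newly above the laboratory's upper limit, and number and percentage at least doubling;
- all of this overall and by Day 1 eGFR (<30, 30–59, ≥60), naming the eGFR formula used.

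State whether the Day 1 CPK sample is pre-dose. The laboratory tables do not say, and the table can be read as change from baseline only if it is.

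The cost is one table from data already collected, with no new testing and no change to N. The downside is that the eGFR groups will be small and some threshold crossings will be noise, so the table is descriptive only. Extending the layout to ALT, AST, AP and bilirubin is optional, because the Phase 2b summary reports no other clinically significant laboratory abnormality.
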